## Improved access to psychological interventions in primary care: feasibility and observational study of a transdiagnostic course for large groups

**Summary**

[In Sweden and many other countries,] primary care is tasked with assessing and treating patients with mild to moderate mental health problems, including the majority of patients with depression and anxiety disorders. Primary care is also tasked with offering prompt access to high quality care. Despite existing guidelines for the management and treatment of mental health problems in primary care, approximately one of three primary care clinics [in Sweden] do not offer assessment or treatment with a psychologist, and the effects of psychological interventions have rarely been evaluated empirically. The aim of this pilot study is to evaluate a transdiagnostic CBT-based large-group intervention in the primary care system of Sweden in terms of feasibility and preliminary efficacy, with British reference data.

**Overview of the field (background)**

The Swedish point prevalence for depression is 11%, and the point prevalence for clinically significant anxiety is about 15% (1). Common mental disorders such as depression and anxiety disorders have been found to be associated with functional impairment and reduced quality of life in a large number of studies (2, 3). A substantial proportion of these patients are in need of assessment and interventions in primary care, and some studies indicate that the majority of patients with mood disorders are found in primary care (4). Of patients seeking help in primary care, approximately 30-50% suffer from a mental health condition (5, 6).

Swedish national board of health and welfare targets dictate that at least 60% of patients with depression are to be offered psychological treatment ([cognitive behaviour therapy:] CBT or [interpersonal therapy:] IPT) and that 70% of patients with clinically significant anxiety are to be offered CBT (7). The task of primary care [in Sweden] is to assess and treat patients with mild to moderate mental health problems, i.e., the majority of patients with depression and anxiety disorders. Primary care is also tasked with offering easy access to high quality care (8). Region Stockholm guidelines prescribe that patients seeking help for mental health problems should be offered treatment with an expert clinician within 3 days (9). Despite this, only about half of primary care clinics [in Sweden] report being able to meet patient demand for mental health care (10) and the effects of psychological interventions have rarely been evaluated (11).

One way of ensuring access to psychological interventions in primary care could be to offer low-intensity interventions, i.e., psychological interventions that require relatively few resources, and interventions that are effective for a wide spectrum of psychiatric problems (12, 13). According to a meta-analysis from 2015 (13), transdiagnostic interventions for depression and anxiety commonly have large within-group effects on anxiety ( $g = 0.85$ ) and depression ( $g = 0.91$ ). In randomised controlled trials, according to the same source, controlled effect versus waitlist controls and attention control conditions are typically moderate to large on anxiety ( $g = 0.70$  and  $0.80$  respectively) and moderate to large on depression ( $g = 1.0$  and  $0.69$  respectively). This implies that a transdiagnostic intervention can be an adequate alternative for many patients where additional interventions are unnecessary.

[Translated from the original that was approved by the Swedish ethical review authority]

One example of a widespread transdiagnostic low-intensity course based on CBT principles for patients with a wide spectrum of mental health problems is the Stress Control intervention (SC) (14, 15). This course is given in a large-group format and consists of six weekly sessions of 90-120 minutes with up to 100 participants. One potential advantage of this type of lecture-format intervention is being able to reach populations that rarely seek psychological care, such as men, individuals with low educational attainment and the elderly. The SC course primarily comprises education about common types of mental health problems including chronic stress disorders, anxiety, depressed mood and disordered sleep. Themes covered are: 1) stress and physical reactions to stress, 2) physical exercise and relaxation, 3) cognitions and how stress affects cognitions, 4) behavioural activation and problem solving, 5) managing panic attacks and 6) sleep and response prevention. (16) The SC intervention has been evaluated as part of the Improving Access to Psychological Therapies (IAPT) national initiative in England to improve access to psychological interventions for patients with mental health problems. Within IAPT, each year, about 537 000 patients are treated for depression and anxiety in accordance with British national guidelines. Interventions within IAPT are systematically evaluated, with pre- and post- treatment data available from 98% of patients (17). Within IAPT, the SC intervention has been found to have a moderate to large within-group effect on anxiety ( $d = 0.70$ ), a moderate effect on depression ( $d = 0.59$ ) and a moderate effect on work-related functional impairment ( $d = 0.47$ ). About 42% of patients with clinically significant symptoms before SC have achieved a clinically significant and reliable improvement at treatment termination (12). This is only marginally lower than corresponding figures from interventions developed for specific mood and anxiety disorders (18, 19).

### ***Research question (study aims)***

The aim of this within-group study is to evaluate a CBT-based intervention similar to SC, focusing on feasibility and efficacy in Swedish primary care, with British reference data (12). The study includes a combination of patients with clinically significant levels of anxiety or depression and patients with subclinical symptoms, analyses concerning the clinical group being the primary focus of the study. The primary outcome is patient satisfaction, see below. Secondary outcomes include adherence to the protocol and effects on psychiatric symptoms in terms of anxiety and depression. Perceived stress, functional impairment and adverse events are also surveyed to make it possible to assess the relevance of the intervention for stress-related mental health problems, enable comparisons versus other protocols and ensure that the intervention is safe and does not result in unnecessary distress. Specific hypotheses are:

- Primary outcome: For patients with clinically significant symptoms, adequate satisfaction as measured using the 8-item Client Satisfaction Questionnaire (CSQ-8) and as evidenced by mean score of at least 22 points.
- Secondary outcome: For patients with clinically significant symptoms, adequate proportion of clinically significantly improved (12), in accordance with Jacobson and Truax (20). At least 1/3 of participants reporting a reliable reduction in anxiety (on the GAD-7) and a GAD-7 score below cut-off (8p) after the course. At least 1/3 of participants reporting a reliable reduction in depression (on the PHQ-9) and a PHQ-9 score below cut-off (10p) after the course.

Exploratory secondary outcomes also include:

- Adherence to the protocol, operationalised as the number of lectures attended.

[Translated from the original that was approved by the Swedish ethical review authority]

- Self-reported lifestyle behaviours at baseline, and change in lifestyle behaviours. Due to limited power, this focuses on within-group effect sizes and not inferential statistics.
- The proportion of patients in need of additional mental health interventions, as determined by a clinician interviewer after the course.
- The proportion of patients who report a perceived need of additional interventions.
- Adverse events during the intervention

### ***Description of the research project (methods)***

#### *Design and power*

This study is a within-group trial (i.e., observational study) where 68 patients with common clinically significant psychiatric problems in terms of anxiety and depression are recruited in the primary care system of Stockholm[, Sweden]. The intervention is evaluated in terms of [satisfaction, ]adherence and self-reported symptom outcomes. Power was determined to enable the analysis of data based on a general linear model with dependent means (pre-post) with 80% power in studying effects on symptoms corresponding to  $d=0.45$  given  $\alpha=0.05$  and the expected data loss (no data at post intervention) of 40%. The effect size  $d=0.45$  was chosen on the basis of effects reported by similar interventions in British primary care (12). Up to 25 patients with subclinical symptoms (PHQ-9<10 and GAD-7<8) are also recruited for an exploratory investigation of satisfaction and preliminary efficacy in this patient group.

#### *Recruitment*

Patients are continuously recruited from routine care at Liljeholmen academic primary care clinic[, Stockholm, Sweden]. Patients scheduled for assessment by the psychosocial team are informed by their physician or nurse about the possibility of taking part in a newly developed transdiagnostic intervention within the context of a study. The patient is then scheduled by a clinician not working as therapist in the study for an eligibility interview with a psychologist student or a mental health clinician at the primary care clinic. The clinician conducting the interview informs the patient about the voluntary nature of study participation and that the study is not part of routine health care. The patient is given a copy of the patient information when the eligibility interview is booked. This gives the patient time to think over the decision to apply for the study, and we therefore believe that there is a smaller risk of patient-therapist-dependency affecting this decision. For the eligibility interview, informed consent is provided before screening.

Eligibility criteria are the following:

1. (I) At least 8 points on the GAD-7 or at least 10 points on the PHQ-9 (n=68) – or (II) below 8 points on the GAD-7 and below 10 points on the PHQ-9 (up to n=25).
2. At least 18 years old
3. Based on a brief structured clinical interview developed specifically for the study, no severe psychiatric condition requiring further assessment or treatment in specialist psychiatry, for example a bipolar disorder, suicidal ideation or a psychotic disorder.
4. Medication with monoamine agonists[, primarily antidepressants, either non-existent or] stable since at least 6 weeks and planned to be stable during the intervention
5. No planned absence two weeks or more during the intended intervention period

### *Intervention*

Patients are enrolled in a CBT-based intervention similar to SC, in a transdiagnostic format that enables shortened clinic waiting times. The course consists of six weekly lectures where up to 50 patients participate over 90 to 120 minutes.

The intervention is primarily based on psychoeducation about stress and how the body reacts to stressors, about exercise/activity and recuperation/relaxation, the impact of behaviours and thoughts on mental health, about anxiety, depression, how to manage sudden burst of intense anxiety (panic attacks) and techniques for improved sleep. The course comprises 6 lectures with corresponding themes: (1) "Stress", (2) "Worry and anxiety", (3) "Low mood and depression", (4) "Sleep", (5) "Physical activity and mental health" and (6) "Relationships and the importance of emotions". The aim of the course is to improve the participants' ability to identify what they need to feel better, and to provide the participants with the tools necessary for them to improve their mood for the better. Structured PowerPoint presentations will be used. The course also involves written material about each lecture theme and this material includes suggestions for tailored exercises ("homework"). Participants are encouraged to read and work with the written material before and between each lecture.

The psychological intervention is led by clinicians of the psychosocial team which consist of counsellors ["kuratorer"] and psychologists with training in cognitive behaviour therapy (CBT). In order to ensure competence, all therapists except the author of the course, [name], attend a half-day introduction to the intervention and also sit in on at least one lecture led by a clinician already trained in delivering the course. All therapists receive regular supervision by the project leader [name] (and [name] by another researcher in the project) about every other week over the course of the study. Adherence is ensured by the use of a structured manual and checklists completed by the therapist after each lecture.

At inclusion and during the course, participants are encouraged to contact clinicians working with the group intervention if symptoms deteriorate. Each week, participants rate their mood including suicidal ideation using validated instruments. Their responses are reviewed by researchers in the project, and participants who experience a substantial deterioration in symptoms are contacted for a discussion about their further participation in the course. Participants also have the opportunity to contact their course leader via the study web page, via a secure system reminiscent of email. If necessary, the intervention is terminated and the participant is referred to routine care services.

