### *Measurements and psychometric instruments*

Assessments in the study are: the screening (for the eligibility interview), the pre-intervention assessment, five weekly measurements during the course (w. 1-5) and the post-intervention assessment. A follow-up assessment will also take place after 3 months. Thus, in total, there are 9 assessment points. The measurements are conducted using online questionnaires that are stored in the patient's digital record.

At the pre-intervention assessment, information is also collected during the eligibility interview. This interview involves questions about sociodemographic variables, a structured questionnaire for the assessment of suicidal ideation and severe psychiatric problems and questions concerning medication.

[Translated from the original that was approved by the Swedish ethical review authority]

At each group session, the participation of each patient is registered. Post intervention, the patient also meets with a clinician of the psychosocial team. This appointment is booked 6 weeks from the planned start of the course. This assessment is conducted in a manner analogous to routine care assessment by the psychosocial team of the primary care clinic. During this assessment, all further necessary arrangements are registered (e.g., no need for further arrangements, referral to psychiatric services or additional help and if so of what kind). The patient also reports on adverse events, satisfaction with the course, changes to medication and other therapies. Lifestyle behaviours are surveyed over the course of the study because little is known about lifestyle behaviours in Swedish primary care patients, and the relation between lifestyle behaviours and mental health has been identified by the Swedish national board of health and welfare as a high-priority topic in primary care research.

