#### *Evaluation and statistical analysis*

Primary outcome is the mean CSQ-8 score for patients completing this post-intervention questionnaire. Secondary outcomes that concern clinically significant improvement are based on the algorithm for reliable change as specified by Jacobson and Truax (20), combined with the established cut-offs for anxiety and depression of 8 points on the GAD-7 and 10 points on the PHQ-9 (27). Clinically significant improvement is calculated based on the last observation from each patient. Dose-response relationships and change over time are analysed using linear mixed models, if deemed suitable for the data. Linear regression is used for other continuous outcomes, and chi tests for nominal data. Within-group effect sizes are presented in terms of Cohen's *d*, and standardised effect sizes are compared to British reference data (12).

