#### *Time plan and feasibility*

From the late summer or early autumn of 2020, recruitment for the study is expected to take ca 6-7 months. Then follows a follow-up period of 3 months, which implies that all data are expected to have been collected around the early summer of 2021. The curation of data, statistical analysis and manuscript writing is expected to take 3 months. In total, the study is expected to be completed in ca 12-15 months and to conclude around the end of 2021.

Liljeholmen primary care clinic is one of the largest primary care clinics in Sweden, with around 30 000 listed patients. The clinic is situated in central Stockholm, with a steady inflow of patients with mental health problems. There is currently a substantial waiting time to meet with a clinician of the psychosocial team. The primary care clinic hosts a large conference room housing up to 50 persons, and the front desk is staffed on the days and nights when the course is expected to take place. The psychosocial team consists of counsellors ["kuratorer"] and psychologists with competence in cognitive behaviour therapy. The project has been designed with the needs of the patients and staff of the primary care clinic in mind, and members of the psychosocial team, other professions and the management team have been involved in the planning of this study. This speaks for the study being completed as planned.

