### ***Significance***

This pilot study is expected to be of great significance in establishing whether the type of SC intervention that has been found successful in England is feasible also in the primary care system of Sweden. If the study is indicative of promising results, the research group is planning to evaluate the effects of the course versus relevant control conditions, probably within the context of a randomised controlled trial. The long-term research question may be whether the evaluated course protocol can serve a similar role as the SC protocol does in England, i.e., as a cost-effective intervention that makes it possible to improve access to psychological treatment in primary care whilst requiring relatively few resources.

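### Does the plan need to allow for course rounds in its sample size, analysis and outcomes?

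*Combined protocol and SAP*

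**What the plan says.** The Intervention section describes the delivery: "The course consists of six weekly lectures where up to 50 patients participate over 90 to 120 minutes". Under Design and power, 68 patients with clinically significant symptoms are recruited, plus up to 25 with subclinical symptoms. The same section states: "Power was determined to enable the analysis of data based on a general linear model with dependent means (pre-post) with 80% power", for d = 0.45, alpha 0.05 and 40% without post-intervention data. Under Time plan and feasibility, "recruitment for the study is expected to take ca 6-7 months".

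The Evaluation and statistical analysis section says that dose-response relationships and "change over time are analysed using linear mixed models, if deemed suitable for the data". It names no term for round or course leader. The aims section sets the success criteria for the clinical group: a mean CSQ-8 of at least 22, and at least one third with reliable improvement and a score below the cut-off on the GAD-7 and on the PHQ-9. Among the exploratory outcomes is "Adherence to the protocol, operationalised as the number of lectures attended". Neither the number nor the size of rounds is an outcome. The Measurements section does provide that "At each group session, the participation of each patient is registered".

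**The concern.** Patients who attend the same course share lecturers, calendar time and fellow participants, so their outcomes may be correlated. Sixty-eight patients do not fit into one course of 50, so the sample is made up of a few rounds. A power calculation and a test that treat patients as independent can then overstate the information in the data.

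There is also a feasibility side. The Summary says that the study is to "evaluate a transdiagnostic CBT-based large-group intervention in the primary care system of Sweden in terms of feasibility and preliminary efficacy". The same 93 patients could sit in 2 rounds of 46 or 47, or in 5 rounds of about 19, and no listed output would tell these apart. A single weak or strong round could also move the primary mean. With equal rounds, one round that scores 4 CSQ-8 points lower (an illustrative figure) shifts the overall mean by 4/2 = 2.0, 4/4 = 1.0 or 4/5 = 0.8 points.

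**Working it through.** **Inputs from the documents.** N = 68 clinical patients (plus up to 25), d = 0.45, alpha = 0.05, loss 40%, at most 50 per course, recruitment over 6-7 months. Sidedness is not stated; two-sided is used because it reproduces N.

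**Assumptions.** ICC of pre-post change 0.01 to 0.05. Rounds k = 2 (the minimum, since 68/50 = 1.36 and 93/50 = 1.86), or 4 to 5 if six-week courses run back to back (26/6 = 4.3, 30/6 = 5.0). Rounds of equal size.

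**Step 1: the plan's figure.** For a two-sided paired t-test with noncentrality d√n, power is 0.793 at n = 40 and 0.803 at n = 41. So 41 pairs are needed, and 41/(1 − 0.40) = 68.3. The stated 68 reproduces, with patients treated as independent.

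**Step 2: a test corrected for clustering.** The design effect is DE = 1 + (41/k − 1) × ICC, and the effective sample size is 41/DE. For k = 2 and ICC = 0.05: DE = 1 + 19.5 × 0.05 = 1.975, effective n = 20.8, power 0.50. Over ICC 0.01 to 0.05, power at d = 0.45 is 0.73-0.50 (k = 2), 0.77-0.63 (k = 4) and 0.77-0.67 (k = 5). These figures describe a test that corrects its standard error with a known ICC. The plan specifies no such test.

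**Step 3: the pooled test.** Simulating the pooled paired t-test on 41 completers (total SD 1, 200,000 runs per cell) gives:

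| Rounds | Power at d = 0.45, ICC 0.01 to 0.05 | Two-sided error, ICC 0.01 to 0.05 |
|---|---|---|
| 2 | 0.78 to 0.74 | 0.07 to 0.16 |
| 4 | 0.79 to 0.76 | 0.06 to 0.11 |
| 5 | 0.80 to 0.77 | 0.06 to 0.09 |

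The approximation 2 × [1 − Φ(1.96/√DE)] gives the same error rates, for example 0.163 for k = 2 and ICC = 0.05. So the main effect of ignoring rounds would be on the error rate, with only a small loss of power.

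**Step 4: possible remedies.**
- A fixed round factor keeps power near 0.80 at ICC 0 (0.802, 0.801 and 0.801 for k = 2, 4 and 5). It does not restore the error rate for the average change: at ICC 0.05 this is 0.169, 0.112 and 0.099.
- A t-test on k − 1 degrees of freedom has power 0.18, 0.50 and 0.59 at d = 0.45, even at ICC 0.
- Adding patients to restore 80% in the Step 2 test would need an ICC that the documents do not give.

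**Step 5: the success criteria.** The mean CSQ-8 and the one-third proportions are compared with fixed thresholds, and no test is stated. Clustering does not bias them. It affects only their precision: at ICC 0.05 and 41 respondents, the standard error grows by √DE = 1.41 (k = 2), 1.21 (k = 4) or 1.17 (k = 5).

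**The case for a change.** The strongest case for acting rests on feasibility, which needs no ICC. The study evaluates a large-group format, so a reader should know how large the groups were, and this matters more because the course was held online and the 50-seat room no longer set the size. One sentence, one table and one sensitivity model cost almost nothing. The independence assumption is also unstated, and pooled p-values would be too small if it fails.

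Part of this stands. Independence is assumed without being said, and a report that gives the number and size of rounds, with CSQ-8 means and symptom change by round, would be better for it. But the attendance register already holds the information about the rounds, and an analyst can tabulate it without a protocol change. Means by round, from about 8 to 20 completers each, would be imprecise. The sensitivity model would not address the error rate, which is the consequence that matters.

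The resource argument reaches beyond this study. The Significance section hopes for an intervention that "makes it possible to improve access to psychological treatment in primary care whilst requiring relatively few resources", but presents this as a possible long-term research question, after mention of a later controlled trial. Resource use and group size are not among this study's outcomes.

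Nor is 80% a firm ceiling. The 40% loss refers to patients without post-intervention data, while the GAD-7 and PHQ-9 are also collected weekly, and a mixed model can use those scores. If 50 patients rather than 41 were informative (an assumption), power under independence would be 0.88.

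**Conclusion.** No change to the plan follows. The observation is accurate: at least two rounds are needed, and the figure of 68 takes patients as independent. Its consequence is not established, because both the ICC and the number of rounds are assumptions. Under ICC 0.01 to 0.05 and 2, 4 or 5 equal rounds, the pooled test loses at most about 6 percentage points of power at d = 0.45 (0.80 to 0.74). Its error could reach about 0.16 in the worst case (2 rounds, ICC 0.05). At the British symptom effects that the background section cites (0.59 and 0.70), even the corrected test of Step 2 keeps power of 0.85 or more with 4 or 5 rounds.

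The inflated error is a reason to read the symptom p-values with care. No available remedy improves on the pooled analysis: the fixed factor does not correct the error, and round-level inference has too little power. The CSQ-8 criterion and the one-third criteria would stay as they are, unbiased. What is left is a sensible reporting choice, namely to describe the rounds in the results and note that p-values assume independence within them. An uncontrolled pilot that leads to a possible randomised trial does not need this written into the plan.
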